#### Lost to follow up

Follow up times for subjects who are in study at the time of analysis will be censored in time-to event analysis, as with time until listing for cardiac transplant. Since the outcome regarding time to listing includes death as part of a compound outcome, there will be no censoring for death. In case of lost to follow up before time of analysis subjects will be censored, unless the investigators feel the subject could have been indicated for transplant in which case they will be included as such in the analysis.

#### Multiplicity

For both the primary analyses of short-term outcomes and the secondary analysis of long-term analyses, there will be one primary (or first) analysis and thus no correction will be made for multiple comparisons. A sequence of outcomes of interest is also given (Sections 3.2 and 3.3) for each of the short and long-term outcomes, and significance will be assessed in the order of these sequences. Therefore, no adjustment is made for multiple testing.

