### 3.2 Short Term Endpoints

The primary short-term efficacy endpoint regarding the cell product and its delivery procedure is:

Change in right ventricular cardiac function at 3 months post-Stage II surgery compared to baseline, measured by *apical fractional area change, circumferential strain, and longitudinal strain on echocardiogram*.

Secondary short-term efficacy and safety endpoints in order of their relevance and importance in this clinical study are:

- 1) Change in cardiac function between baseline and hospital discharge for Stage II surgery, measured by echocardiogram.
- 2) Cumulative days of hospitalization per patient at 1 and 3-months post Stage II surgery.
- 3) Change in weight, heart rate, and oxygen saturation at 3-months post Stage II surgery compared to baseline.

Additional variables may be assessed in an exploratory manner.

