### 3.3 Long Term Endpoints

The primary long-term efficacy endpoint regarding the cell product and its delivery procedure is:

Change in right ventricular cardiac function at 12 months post-Stage II surgery compared to baseline, measured by echocardiogram.

Secondary long-term efficacy safety endpoints in their order of relevance and importance in this clinical study are:

- 1) Change in weight every 6 months post-Stage II surgery compared to baseline.
- 2) Change in heart failure medication taken every 6 months post-Stage II surgery compared to baseline.
- 3) Change in arrhythmia medication taken every 6 months post-Stage II surgery compared to baseline.

- 4) Success of subject being scheduled for Stage III surgical repair.
- 5) Time (days) until listed for cardiac transplantation, or death following the 6-month follow-up.
- 6) Change in right ventricular function at Stage III surgery pre-op work-up compared to baseline, obtained by echocardiogram, cardiac MRI, and cardiac catheterization.

Additional variables may be assessed in an exploratory manner.

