### 7.1 Sample Size Determination

Sample size calculations were performed using alpha = 0.05 and assume equal variance across study arms. With 50 subjects per arm we will have 80% power to detect an effect size as small as 0.57 in difference in cardiac function measures. This is built on the assumption all subjects from both arms have complete data at baseline and 3-month follow-up visits. In the event of attrition or incomplete data in 40% of participants, equal across study arms, the study has 80% power to detect an effect size as small as 0.74 in difference in cardiac function measures.

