### 7.4.4 Long Term Efficacy Analysis

#### Primary Outcome

The analysis of the primary long-term efficacy outcome, apical fractional area change 12 months post-surgery, will be analyzed like the primary outcome of short-term efficacy, regarding both primary and secondary analyses.

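### Section 7.3's reason for making no multiplicity correction covers error within each test sequence but not across the two, and the plan is inconsistent on whether the 12-month FAC test is primary or secondary

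*Combined protocol and SAP*

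**What the plan says.** The Multiplicity paragraph of Section 7.3 treats the short-term and long-term outcomes as two sets. For each, it says, "there will be one primary (or first) analysis and thus no correction will be made for multiple comparisons". Significance is then assessed in the listed order within each set. The same sentence opens by classing the short-term analyses as primary and the long-term analyses as secondary.

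The endpoint sections use the word primary for both sets. Section 3.2: "The primary short-term efficacy endpoint regarding the cell product and its delivery procedure is" change in right ventricular function at 3 months. Section 3.3: "The primary long-term efficacy endpoint regarding the cell product and its delivery procedure is" the same change at 12 months. The Clinical Study Summary repeats both labels. Neither section names FAC alone: 3.2 lists apical FAC with circumferential and longitudinal strain, and 3.3 says only that function is measured by echocardiogram.

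FAC becomes the tested variable in the analysis sections. Section 7.4.3 tests apical FAC at 3 months by ANCOVA, adjusted for its baseline value. Section 7.4.4 refers to "The analysis of the primary long-term efficacy outcome, apical fractional area change 12 months post-surgery" and applies the same method.

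The only alpha is in Section 7.1: "Sample size calculations were performed using alpha = 0.05". It goes with the statement "With 50 subjects per arm we will have 80% power to detect an effect size as small as 0.57", on the assumption that "all subjects from both arms have complete data at baseline and 3-month follow-up visits". Sidedness is not stated.

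**The concern.** A fixed order of testing protects against false positives along one sequence, provided testing stops at the first non-significant result. The plan has two sequences, and the second starts whatever the first one shows. Having one first analysis in each set means having two first analyses in the trial. The stated reason therefore does not support the stated conclusion.

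Whether this affects the primary error rate depends on the status of the 12-month test, and the plan gives two answers. Under Section 7.3 it is secondary. Under the Summary and Sections 3.3 and 7.4.4 it heads its set as primary. If 3-month FAC missed and 12-month FAC gave p<0.05, the plan would not say whether a primary efficacy endpoint had been met or only a secondary result obtained. That should be settled before the data are seen.

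**Working it through.** **Inputs**
- Alpha 0.05, from Section 7.1. Its use for each head test is inferred, because Section 7.3 gives no level.
- 50 per arm with complete data. With 40% incomplete data, 50 × 0.6 = 30 per arm (Section 7.1).
- Standardized detectable effects 0.57 and 0.74 at 80% power (Section 7.1).
- Correlation ρ between the 3-month and 12-month test statistics: not in the documents, so it is assumed and shown over 0 to 0.9.
- A single look at the data.

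**Step 1: reproduce the plan's figures and settle sidedness.** A two-sample t-test at two-sided 0.05 and 80% power has a detectable effect of 0.566 with 50 per arm and 0.736 with 30 per arm, which match 0.57 and 0.74. One-sided 0.05 would give 0.501 and 0.650, which do not. The plan's figures are thus consistent with two-sided 0.05, which is used below.

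**Step 2: error across the two heads.** With no true difference at either time, and each test significant when |Z| > 1.96:

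P(at least one false positive) = 1 − P(|Z₁| ≤ 1.96 and |Z₂| ≤ 1.96), with Z₁ and Z₂ bivariate normal with correlation ρ.

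At ρ = 0 this is 1 − 0.95² = 0.0975. The upper bound for any ρ is 0.05 + 0.05 = 0.10.

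| Assumed ρ | At least one false positive |
|---|---|
| 0 | 9.75% |
| 0.3 | 9.5% |
| 0.5 | 9.1% |
| 0.7 | 8.3% |
| 0.8 | 7.8% |
| 0.9 | 7.0% |

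Counting only false positives in favour of cells, the figures are 4.9%, 4.5% and 3.9% at ρ = 0, 0.5 and 0.8, against 2.5%.

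**Step 3: if only the 3-month test is primary.** There is one primary test, so the single-look error is 5%.

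**Step 4: effect of two possible remedies.**
- Test 12-month FAC for a claim only after a significant 3-month test, both at 0.05. A false positive on either when neither effect exists requires a false positive at 3 months, so the error is 5%. Power at 3 months is unchanged.
- Give each head 0.025. At ρ = 0 the error is 1 − 0.975² = 4.9%; at ρ = 0.5 it is 4.7%. By t-test, power at an effect of 0.57 with 50 per arm falls from 80.6% to about 72%. The detectable effect at 80% power rises to about 0.62 (50 per arm) and 0.81 (30 per arm).

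**The case against.** The strongest reply is that the plan already ranks the two. Section 7.3 calls the long-term set secondary, Section 7.4.3 calls 3-month FAC the primary outcome, Section 7.1 assumes complete 3-month data, and Section 7.4.1 times every interim analysis to the 3-month visit. The 12-month endpoint is only ever called primary within the long-term set. This largely stands. A reader might infer that nothing ranks the two heads, or that the trial's primary error rate is simply 9%. The documents support neither: on Section 7.3's own labels the single-look primary error is 5%, and any figure near 9% needs a correlation that the documents do not give.

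The correlation could also be high. It is the same measure in the same children with the same baseline covariate, and Section 7.3 allows last observation carried forward where appropriate. No echocardiogram is scheduled between 3 and 12 months, so a carried-forward 12-month value would usually be the 3-month one. As an illustration with equal variances, carrying forward 40% of values would turn an underlying correlation of 0.5 into 0.6 × 0.5 + 0.4 × 1 = 0.7, and 9.1% into 8.3%. That lowers the figure but does not bring it to 5%.

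A further reply is that this is an open-label, non-randomized Phase IIb study meant to inform later definitive studies, with short-term and long-term evaluation as distinct aims. That is a fair reason not to demand strict control over every outcome. It does not rescue the argument in Section 7.3, which rests on there being one first analysis rather than on two separate claims.

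A reader might also object that the 12-month test was not sized. Little follows: sizing has no bearing on false-positive risk, and with the same numbers and alpha the detectable standardized effect is the same at 12 months.

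**Conclusion.** The point holds as a gap in the stated reasoning together with an inconsistent label. The argument in Section 7.3 controls error within a sequence, not across the two, and the head of the long-term sequence is secondary in one place and primary in three (the Summary, 3.3 and 7.4.4).

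Its size depends on that label. If both heads are primary, the chance of at least one false positive is about 7.0% to 9.75%, and 9.1% at an assumed correlation of 0.5. If only the 3-month test is primary, it is 5%. These figures assume two-sided 0.05 for each test, a single look and no true difference at either time. Bias from non-random assignment is separate and not included.

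The interim analyses in Sections 7.4.1 and 7.4.2 are also a separate matter. No boundary is stated for the five looks. If each were tested at 0.05 with equal spacing, the 3-month test alone would reach about 14%. The fix below does not change that, and its 5% refers to one look.

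**What to change.** In Section 7.3, replace the reason given for no correction with wording such as:

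> Apical FAC at 3 months is the single primary analysis of the trial, tested at two-sided 0.05. Apical FAC at 12 months is a key secondary test. It supports a confirmatory claim only if the 3-month test is significant; otherwise it is reported as an estimate with a 95% confidence interval.

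Relabel the 12-month endpoint as key secondary in the Summary and in Sections 3.3 and 7.4.4, and name apical FAC there, so that all places agree with Section 7.3. Report the other long-term outcomes as secondary or supportive, with estimates and confidence intervals. Making significance claims on all of them, including transplant listing or death, depend on a 3-month echocardiographic measure is a debatable trade-off and is not needed here.

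The cost is wording in the protocol and SAP: no patients, visits or procedures, and no loss of 3-month power. The downside is that after a 3-month miss, a 12-month p<0.05 is supportive only.

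If the sponsor wants two separate primary claims, the alternative is 0.025 for each, with the detectable effects in Section 7.1 restated as about 0.62 (50 per arm) and 0.81 (30 per arm).

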## 7.4 Analysis

### 7.4.1 Interim Analysis

This study has 5 planned safety and efficacy interim analysis planned. An interim analysis will be performed according to statistical analysis plan on all enrolled subjects after 10, 20, 30, 40 and 50 subjects have been treated and completed the 3-month follow-up visit. Results will be reviewed by the DSMB.

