#### 1.4 Clinical Data to Date

The following is a summary of available data through May 17, 2018 for safety, feasibility, and efficacy from the first ten treated subjects enrolled in the Phase I study and the first three subjects enrolled and accrued in the concurrent observational control study.

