The feasibility of the Phase I study was most significantly compromised by the study inclusion and exclusion criteria. One in every six acceptable autologous products was administered during the Stage II surgery based largely on the narrow Phase I study eligibility criteria. The Phase IIb study has been designed to address the feasibility issue identified in Phase I by requiring fewer exclusion criteria for subject enrollment. It is anticipated that one out of every two subjects with manufactured autologous product will be eligible for enrollment in the treatment arm of this Phase IIb study. Therefore, treating up to fifty subjects under this Phase IIb study should be feasible within a 5-7 site clinical trial.

The feasibility of the Observational study that required prospective data collection for control subjects proved to be highly problematic as recruitment was limited to only three subjects in this time period. The primary limitation to recruitment was in part the bias for eligible subjects to choose to participate in the treatment study. Only a few subjects that met all eligibility criteria and had available UCB product decided to not participate in the Phase I cell-delivery study. Additionally, a significant number of subjects that did not have available autologous product and met all eligibility criteria of the Observational study were unwilling to participate in the Observational study that required multiple non-standard of care clinical visits with additional blood and imaging studies. Therefore, the Phase IIb study was designed with fewer non-standard of care clinical visits to address the feasibility of recruiting a proper control cohort.

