#### **4.3 Enrollment/Procedural Timeout**

Enrollment in either arm of this study will occur at the Procedural Timeout. The Procedural Timeout will be conducted in the operating room, by a trained site investigator, following the completion of the Stage II repair. During the Procedural Timeout, a site investigator will confirm all inclusion and exclusion criteria have been met per Section 4.1 of this protocol and document his/her decision to enroll the subject. If the site investigator determines that the subject, in either arm, fails to meet all inclusion and exclusion criteria, the subject will be declared a screen failure (see Section 4.5) and exited from the study. A subject should not be enrolled in either arm of the study if the subject has surgical complications during the Stage II repair that result in, or could be reasonably expected to result in, significantly decreased cardiac function.

For the treatment group, if a subject is determined to be eligible to enroll, the Procedural Timeout will also include confirmation that the subject's identity matches the patient identifiers on the investigational product label, confirmation of the number of injection sites and product volume to be delivered, and confirmation that there aren't any anticipated complications or concerns.

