#### **4.4 Time of Treatment (Treatment Arm Only)**

For subjects enrolled in the treatment arm, thawing of the product and the cell delivery procedure will occur immediately following the Procedural Timeout. A subject is considered treated at the time that cell delivery injections begin. If only a partial cell delivery occurs, the subject will still be considered treated and will be followed as planned according to the procedures described in

Section 6 of this protocol. The cell delivery procedure will be entered in the eCRF and the reason(s) for failing to deliver a full dose, if applicable, will also be documented in the eCRF.

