### 7.4.2 Final Analysis

The final analysis of the study will be completed no later than after 50 subjects have completed both Treatment (Arm A) and Control (Arm B) of the study. However, the Sponsor may determine according to interim analysis results that both safety and efficacy endpoints have been achieved for the Phase IIb study. The Sponsor can make this determination at any time following the first interim analysis timepoint.

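### Interim efficacy looks are triggered by treated children alone, with no minimum number of controls, and the analysed set is not limited to children whose 3-month window has closed

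*Combined protocol and SAP*

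**What the plan says.** Section 7.4.1 plans five looks, each for both safety and efficacy. Each is run "on all enrolled subjects after 10, 20, 30, 40 and 50 subjects have been treated and completed the 3-month follow-up visit". Section 4.4 fixes the meaning of the key word: "A subject is considered treated at the time that cell delivery injections begin". A control can never be treated in that sense, so the count is of Arm A only. No section states how many controls must be available at a look. By contrast, the final analysis in Section 7.4.2 names both arms.

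The same section says: "An interim analysis will be performed according to statistical analysis plan on all enrolled subjects". Enrollment is a Day 0 event: "Enrollment in either arm of this study will occur at the Procedural Timeout". Section 7.2 narrows the efficacy set to subjects with follow-up data and, in Arm A, full delivery, but does not say that the follow-up must be the 3-month echo. Section 7.3 permits last observation carried forward (LOCF) where it is judged suitable.

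The looks can have consequences. Under Section 7.4.2, "the Sponsor may determine according to interim analysis results that both safety and efficacy endpoints have been achieved for the Phase IIb study", and this may happen at any time after the first look.

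On control recruitment, Section 1.4 reports ten treated Phase I subjects alongside "the first three subjects enrolled and accrued in the concurrent observational control study". It adds: "The feasibility of the Observational study that required prospective data collection for control subjects proved to be highly problematic".

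**The concern.** An efficacy look is a comparison of two arms, and its precision is governed mainly by the smaller one. Here the timing depends on one arm only. The arms recruit by different routes (Section 4.2) under separate caps of 50 (Section 4.5), and nothing paces controls against treated children. A look on which the Sponsor may act could therefore rest on very few controls. A nominally significant difference at such a look must be large to reach significance at all, so the estimate that supports an early claim of success would tend to be exaggerated.

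The second question is who is analysed. If all enrolled children are in scope, some will not have reached month 3. Whether they contribute a value depends on how the follow-up data requirement and the LOCF rule are read, and neither reading is fixed in advance.

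**Working it through.** **Inputs.** From Section 7.1: alpha 0.05, equal variance, 80% power, effect size 0.57 with 50 per arm and 0.74 with 30 per arm (40% attrition). From Section 7.4.1: looks at 10, 20, 30, 40 and 50 treated. From Section 1.4: 10 treated against 3 controls in the earlier studies. Assumed, because the documents do not give them: the number of controls at each look (shown as a range) and the accrual rate.

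**Reproducing Section 7.1.** A two-sample t-test with two-sided alpha 0.05 and the noncentral t distribution gives detectable effects of 0.566 (50 v 50) and 0.736 (30 v 30), matching 0.57 and 0.74. A one-sided test does not reproduce them. The sample size figures are sound.

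**Precision at look 1.** The same formula is applied with unequal n. The 95% CI half-width in SD units is t(0.975, n1+n2-2) × sqrt(1/n1 + 1/n2). For 10 v 3 this is 2.201 × sqrt(1/10 + 1/3) = 2.201 × 0.658 = 1.45.

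| Treated v controls | Detectable effect, 80% power (SD) | CI half-width (SD) | Power for 0.57 |
|---|---|---|---|
| 10 v 3 | 2.03 | 1.45 | 12% |
| 10 v 5 | 1.66 | 1.18 | 16% |
| 10 v 10 | 1.32 | 0.94 | 23% |

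The half-width is also the smallest observed difference that reaches nominal significance. With 3 controls that is 1.45/0.57 = 2.5 times the planned effect; with 10 controls it is 0.94/0.57 = 1.6 times.

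**Later looks.** With 30 treated, the detectable effect is 1.05 SD with 10 controls and 0.74 with 30. With 50 treated, it is 0.99 with 10 controls, 0.66 with 30 and 0.57 with 50.

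**Type I error.** In a simulation of 100,000 runs, five unadjusted looks at 0.05 gave an overall error of 14.3% with equal arms and 14.5% with 3 controls per 10 treated. The imbalance adds about 0.2 percentage points.

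**Children not yet due at look 1.** With annual Arm A accrual r, about 0.25 × r children have been enrolled for less than 3 months when the tenth passes month 3. Their share of enrolled Arm A is 0.25r/(10 + 0.25r).
- r = 14: 3.5 children, 3.5/13.5 = 26%.
- r = 25: 6.25 children, 6.25/16.25 = 38%.

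The upper rate is 50 children in two years, that is, the 6-year study less up to 4 years of follow-up. The lower rate is 50 in about 3.6 years.

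**Can these children enter the analysis?** Section 7.4.3 models 3-month fractional area change by ANCOVA, and a child without that value drops out unless it is imputed. But an echo is done at discharge (Section 6.2.3), active follow-up begins after the surgical hospitalization (Section 3.1.2), and Section 7.2 does not define follow-up data. A discharge echo carried forward under Section 7.3 would therefore be within the text. As an illustration, if those carried values showed no effect and the pending share were equal in both arms, a true 0.57 would shrink to 0.57 × (1 - 0.26) = 0.42 or 0.57 × (1 - 0.38) = 0.35.

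**The case against.** Three objections have force.

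First, a reader might take 10 to 3 as a forecast. The documents do not support that. The ratio comes from a separate Observational study with many non-standard visits. Section 1.4 says this protocol reduced such visits in order to recruit controls, MRI is now required only at baseline (Section 6.5), and 30 to 50 controls are planned. The ratio is one documented scenario, so a range of control counts is the fair presentation. Even so, better recruitment is a hope. No rule protects a look if it fails.

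Second, a reader might infer that few controls make a false declaration of efficacy much more likely. The simulation shows otherwise. The inflation comes from repeated unadjusted looks, which is a separate issue. What stands here is loss of precision and exaggeration of an early estimate.

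Third, a reader might infer that recently enrolled children automatically enter the efficacy comparison. They do not. Looks follow the analysis plan, Section 7.2 requires follow-up data, and ANCOVA omits a child with no 3-month value. Leaving such a child out because surgery was recent is administrative and not in itself a source of bias. The problem arises only if follow-up data is read to include the discharge echo and LOCF is judged suitable. That choice is open, and would be made with interim data in hand.

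DSMB review of each look is a partial safeguard, but the board is advisory (Section 8.13) and no section gives it a minimum number of controls to apply.

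**Conclusion.** The concern holds as a gap in the trigger and an ambiguity in the analysed set. Section 7.4.1 lets an efficacy look on which the Sponsor may act take place with any number of controls. At look 1 the detectable effect runs from 1.32 SD with 10 controls to 2.03 SD with 3, with CI half-widths of 0.94 to 1.45 SD. These figures rest on an unadjusted two-sample comparison with equal variance, as in Section 7.1, and on assumed control counts.

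Separately, Sections 7.4.1, 7.2 and 7.3 do not exclude carrying a discharge echo forward for a child not yet due. At an assumed 14 to 25 treated per year, 3.5 to 6 Arm A children could be in that position at look 1. The 26-38% is a share of enrolled Arm A, not of the efficacy set.

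The change should be made, but it does not call the design or the sample size into question.

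**What to change.** In Section 7.4.1, separate the two purposes.

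1. Keep safety looks on the Arm A count and on all enrolled subjects.
2. Hold an efficacy look only when the number of controls who have completed the 3-month echo also reaches the look number, capped at the planned minimum of 30: 10, 20, 30, 30 and 30. Requiring equal numbers throughout would need 40 and 50 controls at looks 4 and 5. The protocol allows as few as 30, so those efficacy looks might never occur. With the cap, the detectable effects at the five looks are 1.32, 0.91, 0.74, 0.69 and 0.66 SD.
3. At an efficacy look, analyse only children, in either arm, whose 3-month window has closed. State that LOCF is not used for a visit not yet due.
4. Reconcile Section 7.4.1 with Sections 7.2 and 7.3, and define follow-up data for the efficacy set.

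The cost is a change of wording. The downside is that efficacy looks come later if controls lag, which is when an earlier comparison would tell least. Safety looks are not delayed.
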